The change in the gastric emptying rate AUC from baseline to Day 28 will be analyzed in the FAS using an analysis of covariance (ANCOVA) model with treatment group (three levels) and types (IG, DG) as a factor and the baseline GEBT as a covariate. Each of the two primary comparisons (0.1 mg versus placebo, 0.5 mg versus placebo) will be conducted using a two-sided Dunnett's test at the overall alpha=0.05 significance level.

Other efficacy analyses:

All secondary endpoints will be analyzed using the same types of ANCOVA models as described for the primary analysis. Each treated group will be compared to placebo. All secondary analyses will be conducted with no adjustment for multiplicity.

Subgroup analysis:

A subgroup analysis of idiopathic gastroparesis patients compared to diabetic gastroparesis patients will be performed for all efficacy analysis endpoints.

Pharmacokinetic Assessment

Plasma concentrations will be used to estimate the pharmacokinetic parameters for PCS12852 on Day 1 and Day 28 using noncompartmental methods in WinNonlin[®]. The following parameters will be calculated as data permit:

- C_{max}: maximum observed plasma concentration
- T_{max}: time at which the maximum plasma concentration was observed
- $t_{1/2}$: (the apparent first-order terminal elimination half-life)

Version 3.0 14 of 85 20 April 2022

Name of Investigational Product: PCS12852

Name of Active Ingredient: PCS12852

- AUC_{0-last}: the area under the plasma concentration versus time curve, from time 0 to the last measurable concentration
- AUC $_{\infty}$: the area under the plasma concentration vs. time curve from time 0 to infinity
- λ_z : apparent first order terminal elimination rate constant

A dose proportionality analysis will be conducted for log-transformed C_{max} , AUC_{0-last} , and AUC_{∞} using the power model. In addition, the relationship between gastric emptying rate and drug exposure will be assessed, as data permit. Exposure-response for safety measures may also be explored. Details of these analysis will be provided in the Statistical Analysis Plan.

In addition, a population PK model may be used to describe the PK of PCS12852, if appropriate based on the data collected. A previously developed population PK model describing the PK of PCS12852 in patients with functional constipation, using a two-compartment model with first order absorption, may be used to predict the PK in patients in this study.

Safety Analyses:

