4.1 Overall Design

This is a Phase 2A, placebo-controlled, randomized dose response study of the safety, PK, and efficacy of PCS12852 on gastric emptying rate assessed by the GEBT in patients with moderate to severe gastroparesis.

In this study, gastroparesis patients who have successfully completed Screening criteria (Visit 1) will return for a second Screening Visit (Visit 2) where the inclusion/exclusion criteria will be re-evaluated.

Visit 1 will include all safety labs and procedures (including an ECG) as well as the Columbia-Suicide Severity Rating Scales (C-SSRS) assessed by the investigator to confirm that the patient does not have any suicidal tendencies or ideation. If patients still meet study criteria when returning for Visit 2, a GEBT will be performed and the patient will be educated on completion of the ANMS GCSI-DD. Patients will complete the ANMS GCSI-DD for 7 days. The results from both the GEBT and the ANMS GCSI-DD during the Screening period will be considered the baseline values for these assessments.

The GEBT at Visit 2 and Visit 6 will be performed at the sites. Patients will be told to fast overnight (at least 8 hours) prior to coming to the site for the test. The patient will have their glucose tested both before and after the GEBT. The patient must have a fasting blood glucose of \leq 275 mg/dL to proceed with the GEBT. If the patient does not have a FBG \leq 275 mg/dL, they are permitted to come in the following day to perform the GEBT test. If the patient's FBG is not within range at Visit 6, the patient will be sent home with an additional dose of study medication and asked to return the next day to perform the GEBT.

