8.1.2 Secondary Efficacy Assessment – ANMS GCSI-DD

The ANMS GCSI-DD is designed to assess gastrointestinal symptoms associated with IG and DG. The ANMS GCSI-DD symptom assessments are based on a 24-hour recall period to minimize bias in patient recall. The instrument asks patients to rate the severity of five symptoms: bloating (feeling like you need to loosen your clothes), nausea, not able to finish a normal-sized meal, feeling excessively full after meals, and upper abdominal pain. The severity response is rated by the patient as the worst severity of the symptom over the previous 24 hours. The severity of symptom response scale ranges from 0 ("none"), 1 ("mild"), 2 ("moderate"), 3 ("severe") to 4 ("very severe"). In the scoring of vomiting episodes, the number of episodes of vomiting per day is used, with the episodes capped at 4, so that the scoring is similar to the symptom severity scores of the other items. Therefore, vomiting episodes are scored as 0=none; 1=one episode; 2=two episodes; 3= three episodes and 4= four or more episodes.

The ANMS GCSI-DD total gastroparesis symptom daily score is generated by summing the scores on each of the five symptom items and then dividing by 5, that is the number of items within the gastroparesis related symptom score. Thus, the maximum total symptom score could be (5 symptoms * maximum score 4 divided by 5); hence, the maximum score is 20/5=4. The ANMS GCSI-DD gastroparesis symptom daily score can range from 0 to 4. High scores on the ANMS GCSI-DD reflect greater symptom severity. The minimum clinically important difference in the ANMS GCSI-DD score has been estimated to be 0.50.

In addition, overall severity of gastroparesis is assessed. The overall severity of gastroparesis takes into account that other symptoms might impact on a patient's condition.

In this study, the change from baseline over time for the ANMS-GCSI-DD score will be assessed by comparing the following:

Change from baseline in the ANMS GCSI-DD) (i.e. Day-7 to Day -1) (predose) and Day 7 (Day 1 to Day 7)

Version 3.0 46 of 85 20 April 2022

Change from baseline in the ANMS GCSI-DD (i.e., Day-7 to Day -1) (predose) and Day 14 (Day 8 to Day 14)

Change from baseline in the ANMS GCSI-DD (i.e., Day-7 to Day -1) (predose) and Day 21 (Day 15 to Day 21)

Change from baseline in the ANMS GCSI-DD (i.e., Day-7 to Day -1) (predose) and Day 28 (Day 22 to Day 28)

The ANMS-GCSI-DD sub scores will also be assessed as an Exploratory Endpoint:

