9.2.2 Primary Efficacy Analysis

The change in the gastric emptying rate AUC as measured by the GEBT, from baseline to Day 28 will be analyzed in the FAS using an analysis of covariance (ANCOVA) model with treatment group (three levels) as a factor and the baseline GEBT as a covariate. Each of the two primary comparisons (0.1 mg versus placebo, 0.5 mg versus placebo), will be conducted using a two-sided Dunnett's test at the overall alpha=0.05 significance level.

Other efficacy analyses:

Version 3.0 55 of 85 20 April 2022

All secondary endpoints will be conducted using the same approach as described for the primary analysis. Each treated group will be compared to placebo using Dunnett's test. All secondary analyses will be based on the use of two-sided tests at the alpha=0.05 overall level of significance, with no adjustment for multiplicity.

Subgroup analysis:

A subgroup analysis of idiopathic gastroparesis patients compared to diabetic gastroparesis patients will be done for all efficacy analysis endpoints.

Pharmacokinetic analysis:

Plasma concentrations will be used to estimate the pharmacokinetic parameters for PCS12852 on Day 1 and Day 28 using noncompartmental methods in WinNonlin®. The following parameters will be calculated as data permits:

- C_{max}: maximum observed plasma concentration
- T_{max} : time at which the maximum plasma concentration was observed
- t_{1/2}: (the apparent first-order terminal elimination half-life)
- AUC_{0-last}: the area under the plasma concentration versus time curve, from time 0 to the last measurable concentration
- AUC $_{\infty}$: the area under the plasma concentration vs. time curve from time 0 to infinity
- λ_z : apparent first order terminal elimination rate constant

A dose proportionality analysis will be conducted for log-transformed Cmax, AUC0-last, and $AUC\infty$ using the power model. In addition, the relationship between gastric emptying rate and drug exposure will be assessed, as data permit. Exposure-response for safety measures may also be explored.

In addition, a population PK model may be used to describe the PK of PCS12852, if appropriate based on the data collected. A previously developed population PK model describing the PK of PCS12852 in patients with functional constipation, using a two-compartment model with first order absorption, may be used to predict the PK in patients in this study.

Further details of all analyses will be described in the SAP.

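### The GCSI-DD models are not tied to the endpoint's own baseline, and the week-1 mean counts a Day 1 diary entry that includes pre-dose time

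*Combined protocol and SAP*

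**What the plan says.** **Covariate.** Section 9.2.2 specifies the primary model as an "analysis of covariance (ANCOVA) model with treatment group (three levels) as a factor and the baseline GEBT as a covariate". For the secondary endpoints it adds: "All secondary endpoints will be conducted using the same approach as described for the primary analysis". The Synopsis is looser: "All secondary endpoints will be analyzed using the same types of ANCOVA models as described for the primary analysis". The Synopsis primary model also carries gastroparesis type as a factor, which Section 9.2.2 omits. Section 4.1 defines a baseline for both instruments: "The results from both the GEBT and the ANMS GCSI-DD during the Screening period will be considered the baseline values for these assessments". No section enters the GCSI-DD baseline in a model. Section 9.2.4 refers the PAGI-SYM analysis back to the same approach. Section 9.2.2 closes with "Further details of all analyses will be described in the SAP", and Section 9 requires the SAP only before database lock. The text available for review contains no SAP section that settles the covariate.

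**Week 1.** Section 8.1.2 describes the diary item rating: "The severity response is rated by the patient as the worst severity of the symptom over the previous 24 hours". The first secondary endpoint compares the Day -7 to Day -1 diary with week 1, written as "predose) and Day 7 (Day 1 to Day 7". Under Section 4.1 the first dose is given at Visit 3 on Day 1, after a pre-dose PK sample. Section 6.1 has dosing each morning from Day 1. The time of day at which the diary is completed is not stated.

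**The concern.** A change score that is not adjusted for its own baseline keeps avoidable noise, and part of any chance baseline imbalance stays in the treatment difference. With 8 patients per arm such imbalance can be large. The GCSI-DD is the only secondary instrument, and its baseline is already collected. If the model is left open, the covariate may be chosen late in a small trial.

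The Day 1 entry is a separate matter. Its recall window starts before the first dose, yet it is averaged as one of seven treated days, which pulls the week-1 treatment difference toward zero. The exploratory comparison of Day 7 with Day 14 uses the same week-1 mean.

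**Working it through.** **The plan's own figure.** Section 9.3 gives 80% power for 8 per arm, difference 25, SD 15, two-sided alpha 0.025. The noncentrality is 25 / (15 × √(2/8)) = 25 / 7.5 = 3.33. A two-sample t test (14 df) gives 78.4%; the residual df of the three-arm ANCOVA (20) give 81.0%. The figure reproduces, but it concerns the GEBT AUC. No SD, correlation or power is given for the GCSI-DD, so the covariate inputs below are assumptions.

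**Covariate.** Let ρ be the correlation between baseline and follow-up GCSI-DD, and k the baseline SD divided by the follow-up SD (s).

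- Change score with a covariate unrelated to GCSI-DD: variance s²(1 + k² − 2ρk).
- Change score adjusted for its own baseline: variance s²(1 − ρ²).
- Ratio: 1 + (ρ − k)² / (1 − ρ²). With k = 1 this is 2 / (1 + ρ).

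| ρ | k | Variance ratio | CI narrower with own baseline | 8 per arm is worth |
|---|---|---|---|---|
| 0.4 | 1 | 1 + 0.36/0.84 = 1.43 | 16% | 5.6 |
| 0.5 | 1 | 1 + 0.25/0.75 = 1.33 | 13% | 6.0 |
| 0.7 | 1 | 1 + 0.09/0.51 = 1.18 | 8% | 6.8 |
| 0.8 | 1 | 1 + 0.04/0.36 = 1.11 | 5% | 7.2 |
| 0.5 | 0.7 | 1 + 0.04/0.75 = 1.05 | 3% | 7.6 |
| 0.7 | 0.7 | 1.00 | 0% | 8.0 |

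The rows with k = 0.7 matter because entry requires a mean score above 2 on a 0 to 4 scale (Sections 5.1 and 8.1.2), which may narrow the baseline spread. Selection can also lower ρ. If the regression slope ρ/k stays at 0.5 with k = 0.7, then ρ = 0.35 and the ratio is 1 + 0.1225/0.8775 = 1.14.

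If baseline GEBT correlates 0.3 with baseline GCSI-DD, and with follow-up only through it, the k = 1 ratio becomes [2(1 − ρ) − (0.3(1 − ρ))²] / (1 − ρ²). That is 0.9775/0.75 = 1.30 at ρ = 0.5 and 0.5919/0.51 = 1.16 at ρ = 0.7, so the result changes little.

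Chance imbalance: the baseline difference between two arms of 8 has standard error √(2/8) = 0.5 baseline SD. With k = 1 the unadjusted change score carries a share (1 − ρ) of it. At ρ = 0.5 a one-standard-error imbalance moves the treatment difference by 0.25 baseline SD.

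**Day 1.** Let f be the share of the Day 2 to Day 7 mean effect that is missing from the Day 1 entry. The seven-day mean then shows (7 − f)/7 of that effect, a dilution of f/7.

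- f = 1: 1/7 = 14.3%. A difference of 0.50, the minimum important difference in Section 8.1.2, reads as 0.43.
- f = 1/2: 7.1%, read as 0.46.
- f = 1/3: 4.8%, read as 0.48.

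Because each item takes the worst severity in the window, pre-dose symptoms can set the whole entry, so f can exceed the pre-dose share of the 24 hours. It cannot exceed 1 unless the drug worsens symptoms on Day 1. Weeks 2 to 4 contain no pre-dose time.

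**The case against.** The strongest reply on the covariate is that baseline GEBT is the primary endpoint's own baseline. Carrying the same approach over could therefore mean that each endpoint is adjusted for its own baseline. The Synopsis wording is compatible with that, Section 4.1 defines a GCSI-DD baseline, and detail is deferred to the SAP. This stands to the extent that a reader might infer the plan has settled on GEBT for the symptom models; no section says so. It does not remove the point: the only covariate named is GEBT, the Synopsis and Section 9.2.2 already differ on the primary model's factors, and nothing available settles the choice.

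A reader might also infer a fixed precision loss, such as a third more variance. The documents do not support that. It requires ρ = 0.5, equal SDs and an unrelated GEBT, none of which is given, and the entry score bears directly on the equal-SD assumption.

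On Day 1, a reader might treat the entry as an untreated day and 14% as the expected loss. Day 1 is a dosing day and the entry time is unknown, so 14% is a ceiling. The effect is limited to week 1 and is conservative in direction. The protocol puts steady state at about Day 5 (Section 2.1), so week 1 already averages over build-up. All of this stands and limits the size, but any entry made on Day 1 still reaches back before the first dose.

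A six-day week 1 also matches weeks 2 to 4 less well. That is a real but small cost.

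**Conclusion.** Both parts hold, within limits.

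The GCSI-DD covariate is not fixed. The literal reading of Section 9.2.2 gives baseline GEBT, and the Synopsis also permits the own baseline. If the literal model were used, and GEBT is unrelated to GCSI-DD, variance would be about 11% to 43% higher than with own-baseline adjustment for assumed ρ of 0.8 to 0.4 and equal SDs. It would be about 5% higher, or almost unchanged, if selection narrows the baseline spread. A loss of precision is therefore plausible but not established.

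The Day 1 entry dilutes the week-1 effect by at most 1/7 (14%), less if the entry is made late in the day and reflects post-dose symptoms. It acts toward the null and touches one of the four secondary endpoints, plus the exploratory comparison that uses the week-1 mean. Neither part affects the primary AUC comparison. The changes should be made because they are nearly free and close a choice that could otherwise be made late.

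**What to change.** - **Section 9.2.2 and Synopsis:** state that each secondary GCSI-DD endpoint is adjusted for its own baseline, the mean of Day -7 to Day -1, and that PAGI-SYM is likewise adjusted for its Day 1 value. Use the same sentence in both places.
- **Section 8.1.2 and Table 2** (and the matching Synopsis endpoint): define week 1 as the mean of Day 2 to Day 7, with Day 1 to Day 7 as a pre-specified sensitivity analysis.
- **Section 8.1.2:** state the time of day for the diary entry. A Day 2 entry is wholly post-dose only if it is made at least 24 hours after the first dose, so the revised window depends on this.

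**Cost:** a few sentences and no new data. Replacing one covariate with another uses no extra degree of freedom. Week 1 rests on six diary days instead of seven. The changes should be in place before unblinding.

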- Change from baseline in the ANMS GCSI-DD (i.e., Day-7 to Day -1) (predose) and Day 21 (Day 15 to Day 21).
- Change from baseline in the ANMS GCSI-DD (i.e., Day-7 to Day -1) (predose) and Day 28 (Day 22 to Day 28).

Exploratory Endpoints

- Change from baseline in ANMS GCSI-DD score over time (Day 7, 14, 21, 28) by comparing Day 7 to Day 14, Day 14 to Day 21 and Day 21 to Day 28.
- Change from baseline in the subscores (nausea, early satiety, postprandial fullness, upper abdominal pain and number of vomiting episodes) of the ANMS-GCSI-DD over time (Day 7, 14, 21, 28) by comparing Day 7 to Day 14, Day 14 to Day 21 and Day 21 to Day 28.
- Change from baseline in PAGI-SYM and PAGI-QOL scores over time by comparing Day 1 to Day 28.
- Change from baseline in Clinical Global Impression-Severity (CGI-S) and Clinical Global Impression-Improvement (CGI-I) scores over time by comparing Day 1 to Day 28.
- Change from baseline in PGI-S and PGI-C scores over time by comparing Day 1 to Day 28.

Safety Endpoints

- Adverse Events (AEs) (by type, severity, and relatedness) at each visit.
- Changes in safety clinical laboratory testing and vital signs at each site visit.
- Changes in ECGs at each site visit and the potential correlation of the PK with changes in the ECG.
- Change from baseline in the C-SSRS scores over time by comparing Day 1 to Day 28.

STATISTICAL ANALYSES:

Analysis Sets:

- Safety Set: All patients enrolled in the study who received at least 1 dose of treatment.
- PK Analysis Population: Patients in the Safety Set with at least 1 plasma sample with a quantifiable concentration of PCS12852.

Version 3.0 13 of 85 20 April 2022

Name of Investigational Product: PCS12852

Name of Active Ingredient: PCS12852

• Full Analysis Set (FAS): All patients who are randomized.

Other populations (e.g., Per Protocol) may be defined and used as supportive evidence of treatment benefit.

Patient Characteristics:

Baseline demographics and disease characteristics will be presented for each treatment group by descriptive statistics. All descriptive summary statistics of continuous variables will include n, mean, median, standard deviation (SD), minimum and maximum. All descriptive summaries presenting frequencies and incidences will include n, percent of total, and N, where N is the total number of patients with recorded values in the corresponding group. Patient completion status and exposure outcomes will be similarly presented.

Primary Efficacy Analyses:

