1.2 Schedule of Activities (SoA)

 Table 1
 Schedule of Activities (SoA)

Procedure	Visit 1 (Screening)	Visit 2 (Screening) (Baseline)	Visit 3 (Randomization) Day 1	Visit 4 Day 7	Visit 5 Day 14	Visit 6 Day 28	Visit 7 48-72 hrs after Day 28 visit	Visit 8/ET Day 35
Visit Window	Days -	21 to -1		±2 days	+3 days	+1 day	_	±1 day
Informed consent	X							
Demographic information	X							
Medical history	X							
Inclusion/ Exclusion criteria	X	X	X					
Screening Lab testing (inc. Hep B/C, HIV and TB)	X							
Concomitant Medications	X	X	X	X	X	X		X
Vital signs	X	X	X	X		X		X
Physical exam ^g	X		X	X	X	X		X
¹³ C GEBT		X				X ^d		

Procedure	Visit 1 (Screening)	Visit 2 (Screening) (Baseline)	Visit 3 (Randomization) Day 1	Visit 4 Day 7	Visit 5 Day 14	Visit 6 Day 28	Visit 7 48-72 hrs after Day 28 visit	Visit 8/ET Day 35
Visit Window	Days -	21 to -1		±2 days	+3 days	+1 day		±1 day
ANMS GCSI-DD ^a		X	X	X	X	X		
Safety laboratory testing				X		X		X
Pregnancy test ^b	X		X	X	X	X		X
ECG ^h	X		Xi	X ^j	Xj	X		X e
C-SSRS	X		X	X	X	X		X
PGI-S			X			X		X
PGI-C			X			X		X
PAGI-SYM			X			X		
PAGI-QOL			X			X		
CGI-S			X			X		X
CGI-I			X			X		X
Adverse Events	X	X	X	X	X	X		X
Study Drug Dispensed			X	X	X	X		

Procedure	Visit 1 (Screening)	Visit 2 (Screening) (Baseline)	Visit 3 (Randomization) Day 1	Visit 4 Day 7	Visit 5 Day 14	Visit 6 Day 28	Visit 7 48-72 hrs after Day 28 visit	Visit 8/ET Day 35
Visit Window	Days -2	21 to -1		±2 days	+3 days	+1 day		±1 day
Study Drug Instructions	X	X	X					
Study Drug Administered			X			X ^c		
PK sample ^f			X			X	X^k	
Drug Accountability				X	X	X		

- a. ANMS GCSI-DD will be collected for 7 consecutive days after Screening Visit 2, but prior to randomization (i.e. from Days -7 to -1) as well as from Day 1 to Day 28.
- b. For WOCBP: Serum β-HCG at Screening Visit 1; Urine pregnancy test at subsequent visits
- c. Patients will take the dose of PCS12852 or placebo in clinic on Day 28.
- d. A blood glucose finger stick will be taken both before and at the completion of the GEBT.
- e. Repeat ECG at Visit 8, only if ECG at Visit 6 was abnormal.

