 To evaluate the effect of different doses of PCS12852 on the gastric emptying rate, as measured by the GEBT, in patients with moderate to severe idiopathic gastroparesis (IG) or DG To evaluate the PK profile of PCS12852 at different dose levels. 	 Change in gastric emptying rate from baseline as determined by the AUC of the gastric emptying rate over time as assessed by the GEBT at Visit 6 (Day 28) after administration of the PCS12852 or placebo. Change in gastric emptying rate from baseline using the t₁₀ and t₅₀ metric for gastric emptying rate. Concentrations of PCS12852 in plasma; PK parameters will be estimated from concentration-time data using noncompartmental methods, as data permit. 			
Secondary				
To evaluate the effects of different doses of PCS12852 on symptoms, as measured by the American Neurogastroenterology and Motility Society Gastroparesis Cardinal Symptom Index Daily Diary (ANMS GCSI-DD), in patients with moderate to severe idiopathic and diabetic gastroparesis	 Change from baseline in the ANMS GCSI-DD) (i.e., Day-7 to Day -1) (predose) and Day 7 (Day 1 to Day 7) Change from baseline in the ANMS GCSI-DD (i.e., Day-7 to Day -1) (predose) and Day 14 (Day 8 to Day 14) Change from baseline in the ANMS GCSI-DD (i.e., Day-7 to Day -1) (predose) and Day 21 (Day 15 to Day 21) Change from baseline in the ANMS GCSI-DD (i.e., Day-7 to Day -1) (predose) and Day 28 (Day 22 to Day 28) 			
To evaluate the effects of different doses of PCS12852 on symptoms or QOL, as measured by the PAGI-SYM, PAGI-QOL, PGI-S, PGI-C, CGI-S and CGI-I, in patients with moderate to severe idiopathic or diabetic gastroparesis	 Change from baseline in ANMS GCSI-DD score over time (Day 7, 14, 21, 28) by comparing Day 7 to Day 14, Day 14 to Day 21 and Day 21 to Day 28. Change from baseline in the sub scores (nausea, early satiety, postprandial fullness, upper abdominal pain and number of vomiting episodes) of the 			

Version 3.0 28 of 85 20 April 2022

Objectives	Endpoints
	ANMS-GCSI-DD over time (Day 7, 14, 21, 28) by comparing Day 7 to Day 14, Day 14 to Day 21 and Day 21 to Day 28.
	Change from baseline in PAGI-SYM and PAGI-QOL scores over time by comparing Day 1 to Day 28.
	Change from baseline in Clinical Global Impression-Severity (CGI-S) and Clinical Global Impression-Improvement (CGI-I) scores over time by comparing Day 1 to Day 28.
	Change from baseline in PGI-S and PGI-C scores over time by comparing Day 1 to Day 28.

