6.7.3 Rescue Medicine

Use of medications that may impact efficacy evaluations is strongly discouraged at any time after Visit 1 in the study. However, patients who experience severe symptoms of gastroparesis after entering the Treatment Period may receive a single day of treatment per week with an anti-emetic drug, but should avoid such treatment, if possible, on the day prior to and day of treatment visits. If a patient requires an anti-emetic drug (e.g., 5-HT₃ receptor antagonists, NK1 receptor antagonists) for more than 1 day a week, or requires an antiemetic drug once weekly repeatedly (i.e., more than 2 weeks while on study), the Investigator should contact the Medical Monitor to discuss the safety of the patient continuing in the study.

The following rescue medications may be used:

- ondansetron or promethazine (tablet, syrup or suppositories) for emesis
- loperamide for diarrhea
- Tramadol for pain

The date and time of rescue medication administration as well as the name and dosage regimen of the rescue medication must be recorded.

7 Discontinuation/Withdrawal Criteria

It may be necessary for a patient to permanently discontinue study treatment. Reasons for discontinuation from study treatment and/or the study may include the following:

- Adverse event
- Death
- Failure to meet randomization criteria
- Lack of efficacy
- Lost to follow-up
- Investigator decision
- Pregnancy

Version 3.0 42 of 85 20 April 2022

- Protocol deviation
- Screen failure
- Site terminated by the Sponsor
- Study terminated by the Sponsor
- Withdrawal by the patient

The reason for discontinuation should be clearly documented on the appropriate eCRF. Discontinuation of study treatment also requires discontinuation from the study. If study treatment is permanently discontinued, the patient will not remain in the study. See the SoA (Table 1) for data to be collected at the time of discontinuation of study treatment and follow-up and for any further evaluations that need to be completed.

A patient may withdraw from the study at any time at their own request or may be withdrawn at any time at the discretion of the Investigator for safety, behavioral, or compliance reasons. The patient will be permanently discontinued from the study treatment and the study at that time.

If the patient withdraws consent for disclosure of future information, the Sponsor may retain and continue to use any data collected before such a withdrawal of consent.

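### As written, the Day 21 and Day 28 symptom-diary ANCOVAs cannot use early leavers, which can bias those estimates when exit depends on symptoms and differs between arms

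*Combined protocol and SAP*

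**What the plan says.** The sole secondary objective is the effect of each dose on symptoms. Table 2 in Section 3 and the Synopsis split it into four endpoints, one per treatment week, the last being "Change from baseline in the ANMS GCSI-DD (i.e., Day-7 to Day -1) (predose) and Day 28 (Day 22 to Day 28".

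On the method, the Synopsis states "All secondary endpoints will be analyzed using the same types of ANCOVA models as described for the primary analysis". Section 9.2.2, under its other efficacy analyses, states "All secondary endpoints will be conducted using the same approach as described for the primary analysis", with each dose compared with placebo by Dunnett's test. The primary model is an ANCOVA of one change score on treatment and baseline. The Synopsis adds gastroparesis type as a factor; Section 9.2.2 does not.

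Footnote a of Table 1 has the diary collected in the week before randomization "as well as from Day 1 to Day 28". Section 7 states "Discontinuation of study treatment also requires discontinuation from the study" and names adverse event and lack of efficacy among the possible reasons for stopping. Section 7.2 gives early leavers the Visit 8 procedures, and Table 1 marks no diary at Visit 8/ET.

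The Full Analysis Set (Section 9.1, Table 5) is everyone randomized. The only missing-data rule in the documents is the item-level half-scale rule for the PAGI-SYM (Sections 8.1.3.1 and 9.2.4). Further detail is left to an SAP whose text is not in the file.

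**The concern.** An ANCOVA of the week-4 change needs a week-4 score. A patient who stops after week 2 has none and contributes nothing to the week-3 and week-4 models unless a rule supplies a value. That patient's week-1 and week-2 scores are recorded and would be expected to predict the later ones, but the stated models have no place for them. The comparison becomes one among patients who stayed, while the objective and the Full Analysis Set concern the randomized groups.

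The GEBT is different: it has one scheduled post-baseline test, so an early leaver has no intermediate values to borrow from. For the diary the information exists and goes unused.

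At stake is how the symptom effect at Days 21 and 28 is read. With 8 patients per arm, one leaver is 1/8 = 12.5% of an arm.

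**Working it through.** **1. The plan's own figure.** Section 9.3 gives 80% power for the GEBT AUC with 8 per arm, difference 25, SD 15 and two-sided alpha 0.025. The noncentrality is 25 / (15 × √(2/8)) = 25 / 7.5 = 3.33. Noncentral-t power is 78.4% on 14 df and 81.0% on 20 df, so the figure reproduces. No corresponding figure is given for the diary.

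**2. Inputs for the diary.**
- From the documents: 8 per arm, four weekly changes, and a minimum clinically important difference of 0.50 (Section 8.1.2), used here as the true Day 28 effect. Improvement is negative, so the true value is −0.50.
- Assumed: SD of weekly change 0.6 to 1.0, correlation ρ between adjacent weeks 0.6 to 0.9 (AR(1)), and the dropout patterns below.

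**3. One placebo leaver, by hand.** Let the worst of 8 placebo patients at week 2 leave. The expected largest of 8 standard normal values is 1.424, so the other 7 sit 1.424 / 7 = 0.203 SD too low at week 2. Two weeks later a fraction ρ² of that remains, so

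shift at week 4 = 0.203 × ρ² × SD

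- SD 0.6, ρ 0.6: 0.203 × 0.36 × 0.6 = 0.044
- SD 0.8, ρ 0.8: 0.203 × 0.64 × 0.8 = 0.104
- SD 1.0, ρ 0.9: 0.203 × 0.81 × 1.0 = 0.164

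The placebo mean looks too good, so the effect moves toward zero by about 0.04 to 0.16. If instead the worst patient of an active arm leaves, the shift has the same size and the opposite sign. If each arm loses its worst patient, the shifts cancel.

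**4. Simulation of the same patterns** (three arms of 8, SD 0.8, ρ 0.8). The repeated-measures estimate is the likelihood fit that uses the earlier weeks.

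| Worst patients leaving after week 2 | Day 28 effect, no dropout | Separate ANCOVA | Repeated measures |
|---|---|---|---|
| 1 placebo | −0.49 | −0.39 | about −0.50 |
| 2 placebo | −0.50 | −0.32 | about −0.50 |
| 1 in each active arm | −0.51 | −0.61 | about −0.50 |

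With one leaver in every arm, the ANCOVA bias was at most 0.004 in all nine SD and correlation combinations.

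**5. Less extreme dropout.** A second, large-sample simulation made leaving after weeks 1 to 3 probabilistic, with log-odds rising by 2 per point of worse weekly score (SD 0.8, constant correlation 0.7, one active arm and placebo).

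| Dropout | Shift toward zero at 10%, 20%, 30% |
|---|---|
| Unrelated to symptoms | 0, 0, 0 |
| Symptom-driven, both arms | 0.03, 0.06, 0.07 |
| Symptom-driven, placebo only (rate in placebo) | 0.08, 0.14, 0.21 |
| Symptom-driven in both arms plus random AE exits on active (rate in placebo) | 0.03, 0.05, 0.06 |

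The both-arms case is not zero because placebo, having worse scores, loses more patients (24% against 16% at an overall 20%). The repeated-measures fit stayed at about −0.50 throughout.

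**6. Against sampling error.** With complete data and SD 0.8, the standard error of the Day 28 difference is about 0.8 × √(2/8) = 0.40. A bias of 0.10 is a quarter of that. With one placebo leaver at ρ 0.8, the root mean squared error is about 0.43 for the ANCOVA and 0.42 for repeated measures.

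**The case against.** Four objections carry weight.

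- **Complete-case analysis is an inference.** The documents never prescribe deleting early leavers. Section 9 calls itself a summary and defers detail to an SAP to be finalized before database lock. This stands: what can be said is that the stated models, with no diary missing-data rule, cannot use a patient without that week's score. The SAP could add a rule. However, it is described as elaborating the analyses in Section 9, and those are ANCOVAs.
- **Bias is conditional.** A reader might infer that the Day 21 and Day 28 estimates are biased, or that the drug effect will be understated. The documents support neither. They give no dropout rate and no sign of imbalance, and Section 7 only lists reasons that may apply. The bias is zero without dropout, and its sign depends on which arm loses its worst patients.
- **The effect is modest against the noise.** These are secondary endpoints, unadjusted for multiplicity, in a 24-patient Phase 2a trial. Under the SD 0.8 assumption, power for a true 0.50 is about 15% even with complete data. This stands and limits the priority of the change.
- **The check favours the proposed model.** Simulated exit depended only on observed scores, so that model's assumption held by construction. The check used likelihood point estimates; the small-sample behaviour of an unstructured Kenward-Roger model was not tested. Hence the fallback structure and sensitivity analyses in the fix.

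**Conclusion.** The point holds in conditional form. The stated weekly ANCOVAs leave out early leavers at Days 21 and 28 while their earlier scores go unused, and this can bias the dose-versus-placebo estimates when exit depends on symptoms and differs between arms.

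For a true effect of 0.50, the illustrative size is about 0.04 to 0.16 points with one worst-case placebo leaver and about 0.03 to 0.07 with symptom-driven dropout in both arms. Both ranges rest on assumed SDs, correlations and dropout patterns. Larger figures can be produced: two placebo leavers at SD 1.0 and ρ 0.9 give 62% of 0.50, or 0.31. That requires exactly the two worst of 8 placebo patients to leave and should not be read as an expectation.

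The primary GEBT analysis is not affected. The change is a cheap improvement; it does not repair a demonstrated error.

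**What to change.** In the Synopsis, Sections 9.2.2 and 9.2.3, and the SAP:

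- Analyze weekly ANMS GCSI-DD change at weeks 1 to 4 in one mixed model for repeated measures in the Full Analysis Set. Include treatment, week, treatment-by-week, gastroparesis type, type-by-week, baseline and baseline-by-week.
- Use an unstructured within-patient covariance with Kenward-Roger degrees of freedom, and pre-specify a simpler structure in case of non-convergence.
- Report the same dose-versus-placebo contrasts at Days 7, 14, 21 and 28, with the Dunnett comparison already stated in Section 9.2.2.
- State how a partly completed diary week is scored; a mid-week exit creates one.
- Keep the weekly ANCOVA as a sensitivity analysis, and add one for dropout that depends on unobserved scores.

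The cost is wording only, with no new patients, visits or data. With complete data the weekly estimates equal those of separate ANCOVAs with the same covariates, here the Synopsis model with type. The downsides are 4 × 5 / 2 = 10 covariance parameters to estimate from about 24 patients, and the assumption that dropout depends on observed scores.
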